#### Hypotheses

• *Null Hypothesis*: Treatment application of the Erchonia Violet ZERONA® Z6 OTC is inferior to treatment application of the Erchonia® Zerona® Z6 OTC in effecting a clinically meaningful reduction in body circumference.

Ho:  $\mu$  < -3.53 inches

• *Alternative Hypotheses*: Treatment application of the Erchonia® Violet ZERONA® Z6 OTC is NOT inferior to treatment application of the Zerona® Z6 OTC in effecting a clinically meaningful reduction in body circumference.

H1:  $\mu \ge -3.53$  inches

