#### PRIMARY EFFICACY OUTCOME

The primary efficacy outcome for this clinical study is the mean change in combined waist-hipsbilateral thighs circumference measurement at study endpoint (following completion of the sixth and final treatment administration procedure) relative to baseline (pre-procedure).

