#### PRIMARY EFFICACY OUTCOME EVALUATION

To determine primary efficacy outcome success, the mean change across all subjects enrolled in this study in combined waist-hips-bilateral thighs circumference measurements at study endpoint relative to baseline will be calculated and compared to the relative mean change attained for treated subjects in the reference study.

As this study is a non-inferiority design, the research hypothesis is that violet diode therapy with the Erchonia Violet ZERONA® Z6 OTC is either equivalent to, or superior to, red diode therapy with the Erchonia Zerona® Z6 OTC in effecting a clinically meaningful reduction in body circumference.

The selected equivalence margin ( $\delta$ ) is ±5%. Therefore, non-inferiority will be established if the mean change in combined circumference measurement for subjects treated with the violet diode laser in the current study is no more than 5% less than the subject group who received treatment with the red diode laser in the predicate reference trial that supported efficacy of the Zerona® Z6 OTC device (K143007).

In the predicate reference study, the mean change in combined circumference measurements across the same 6-treatment 2-week evaluation period was a decrease of 3.72 inches. Therefore, success for the current study will be determined as having been met if the mean change in combined circumference measurements for the subject group in the current study is  $-3.72\pm5\%$  inches (-3.53 to -3.91 inches). This is defined as the maximally clinically acceptable difference for which the range of efficacy values ( $\pm5\%$ ) are "close enough" to be considered equivalent.

Version 1.0

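### The inequality signs in the primary null and alternative hypotheses contradict their own labels on the change-from-baseline scale, because the plan never states its sign convention

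*Combined protocol and SAP*

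**What the plan says.** The SAP's Primary Efficacy Outcome section defines the outcome as the mean change in combined circumference "at study endpoint (following completion of the sixth and final treatment administration procedure) relative to baseline (pre-procedure"). The next section, Primary Efficacy Outcome Evaluation, reports that the reference study's mean change "was a decrease of 3.72 inches" and carries that figure forward as -3.72. It sets the success range at -3.72 plus or minus 5%, printed with a minus sign directly before "3.53 to -3.91 inches". In words, non-inferiority holds if the violet-laser mean change "is no more than 5% less than the subject group who received treatment with the red diode laser".

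The Hypotheses section then pairs words with symbols:

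- Null: the violet device "is inferior to treatment application of the Erchonia® Zerona® Z6 OTC in effecting a clinically meaningful reduction in body circumference", with "H o : $\mu$ < -3.53 inches".
- Alternative: the violet device "is NOT inferior to treatment application of the Zerona® Z6 OTC in effecting a clinically meaningful reduction in body circumference", with "H 1 : $\mu \ge -3.53$ inches".

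Supportive Secondary Evaluations, item (ii), defines a responder in words as a subject who loses 3.0 inches or more, and gives the symbolic form as ≥ -3.0 inches. The Regulatory Background section mixes signs: it reports one mean reduction as -3.7 inches and another as 3.5 inches.

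**The concern.** On a scale where a reduction is negative, values below -3.53 are larger reductions than the boundary and values above it are smaller ones. The printed null therefore collects the good results under the inferior label, and the printed alternative collects the poor ones under the non-inferior label.

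These are the only symbolic hypotheses for the only primary endpoint, in a study meant to support a 510(k) submission. A one-sided test programmed from them as printed would run in the wrong direction. The responder criterion is more exposed, because it is a planned subject-by-subject classification that someone has to code. Under Study Blinding the statistician is not to know which data set is the current study, so an unambiguous written rule matters more than usual.

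**Working it through.** **Inputs.** Reference mean change -3.72 inches, margin 5% and success range -3.53 to -3.91 (Primary Efficacy Outcome Evaluation). Printed hypotheses (Hypotheses). Responder threshold of 3.0 inches, reference rate 73% and acceptable range 68% to 78% (Supportive Secondary Evaluations). 22 treated reference subjects and a sham mean decrease of 0.68 inches in the earlier randomised trial (Regulatory Background).

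**Step 1: reproduce the plan's bounds.**

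- Margin: 0.05 × 3.72 = 0.186 inches.
- Smaller-reduction bound: -3.72 + 0.186 = -3.534, printed as -3.53 (a difference of 0.004).
- Larger-reduction bound: -3.72 - 0.186 = -3.906, printed as -3.91.

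The bounds reproduce. The fault is in direction only.

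**Step 2: place example values.** The hypothesis columns show which hypothesis a mean of that size belongs to. Only the range column is a success rule that the plan states.

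| Mean change (inches) | Printed symbols, read literally | Success range | Signs reversed |
|---|---|---|---|
| 0 (no change) | Not inferior | Fail | Inferior |
| -0.68 (sham mean) | Not inferior | Fail | Inferior |
| -3.00 | Not inferior | Fail | Inferior |
| -3.53 | Not inferior | Success | Not inferior |
| -3.72 (reference mean) | Inferior | Success | Not inferior |
| -3.91 | Inferior | Success | Not inferior |
| -4.00 | Inferior | Fail | Not inferior |

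The printed alternative covers -3.53 and everything above it. The success range runs from -3.91 to -3.53. They share the single point -3.53.

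**Step 3: try a magnitude reading.** If ≥ -3.53 means a reduction of at least 3.53 inches, the alternative becomes reduction ≥ 3.53 and the null becomes reduction < 3.53. Every row then agrees with the verbal labels and matches the last column. This is very probably what was meant, but the plan does not say so.

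**Step 4: apply the literal reading to the responder rule.** Change ≥ -3.0 counts a subject with no change as a responder and a subject with -4 as a non-responder. A 73% rate among 22 subjects corresponds to about 16 responders (16/22 = 72.7%); the count of 16 is inferred, not stated. Literal coding would return the complement, 6/22 = 27.3%, plus any subject at exactly -3.0.

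**Step 5: look beyond -3.91.** With the signs reversed, the hypotheses agree with the success range down to -3.91 and differ beyond it. At -4.00 the range records a failure although the reduction exceeds the reference. Expected Results and Primary Efficacy Outcome Evaluation both say that superior results are meant to count.

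**The case against.** The best defence is that the intent is not in doubt. The hypotheses are labelled in words, the 5% rule is stated in words and numbers, and the -3.53 boundary also appears in the success range. The responder definition shows the convention in use, with the words beside the symbols, and listing the success range from smaller to larger reduction fits it. The mixed signs come from background narrative, not from the SAP. No test of the printed null is specified, so no planned primary calculation uses the symbols. On this view the point is editorial.

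Much of that stands. The signs alone do not change the planned primary verdict. The reference rate of 73% is a fixed comparator, so 27% only illustrates what literal coding would do to a group responding at that rate. The two-sided success range is a separate matter: it conflicts with the superiority wording whichever way the signs are read. A one-sided success rule would change the primary criterion and so is more than a typographical correction.

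The defence does not remove the contradiction. Using an unstated convention twice does not define it, and it departs from the ordinary ordering of signed numbers. The formal hypotheses for the sole primary endpoint should not need to be interpreted against their own symbols.

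**Conclusion.** The concern holds and should be fixed. On the signed change scale that the plan itself uses, both primary inequalities are reversed relative to their labels. The null takes in the reference mean of -3.72, the alternative takes in zero change, and only -3.53 satisfies both the printed alternative and the success range. The responder criterion carries the same fault; a group with a true 73% rate would be reported at about 27%, outside the 68% to 78% range.

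This is a defect of notation, not evidence that the wrong analysis would be run. The conclusion rests on reading the symbols as ordinary signed inequalities, which is the default when no other convention is declared. The responder illustration also rests on the inferred 16 of 22.

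**What to change.** 1. State once that change is endpoint minus baseline and that a negative value is a reduction.
2. Print H0: mu > -3.53 inches (inferior) and H1: mu <= -3.53 inches (not inferior). Equivalently, code reduction as positive, with H0: reduction < 3.53 and H1: reduction >= 3.53. Both keep the plan's placement of the boundary in the alternative. A non-inferiority null conventionally includes its margin, so the authors should confirm that placement.
3. Give the margin as 0.186 inches and say whether the boundary is the rounded -3.53 or the exact -3.534. A mean of -3.532 would pass the first and fail the second.
4. Write the responder criterion as change <= -3.0 inches.
5. Reconcile the one-sided alternative with the two-sided success range. Success at a mean change of -3.53 or below would match the stated non-inferiority aim. Because this alters the success criterion, it should be decided explicitly and before the endpoint data are examined.

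The cost is three inequality signs, one line on the convention and margin, and one sentence on the success range. No subjects, data or time are needed.

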#### SUPPORTIVE SECONDARY EVALUATIONS

The following two secondary evaluations will be performed to provide direct support for the primary efficacy evaluation outcome are will therefore be assessed with respect to statistical significance of change and/or against pre-determined non-inferiority success criteria.

- (i) T-test for independent samples will be performed to compare the mean change in combined circumference measurements across study evaluation (at endpoint relative to baseline) for subjects treated with the Violet ZERONA® Z6 OTC in the current study to the relative mean change for subjects treated with the ZERONA® Z6 OTC in the reference study treatment group. i.e., between device treatment groups. A finding of the difference being not statistically significant (p>0.05) will provide statistically significant and clinically meaningful support for the equivalency of the efficacy of the two devices.
- (ii) Responder rate analysis will be conducted wherein individual responder success is defined per the reference study as at least a 3.0-inch reduction (≥-3.0 inches) in combined circumference measurements for the waist, hips, and bilateral thighs from baseline to after study treatment completion. The maximally clinically acceptable difference for which the responder rate for the current study subject group is defined is (±5%), that is, 73% +/- 5% (68% - 78%), as the responder rate attained in the reference study was 73%.

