Both the predicate and the subject laser devices have the same treatment protocol as will be evaluated for the Violet ZERONA® Z6 OTC in this current study: 6 treatments occurring over 2 weeks: 3 treatments per week; each treatment every other day.

Therefore, as usability has already been established, and all other variables of device user, use, and application are held constant, the goal of this study is solely to demonstrate that efficacy of application of violet light over 20 minutes per treatment administration procedure using the Erchonia ZERONA® Violet Z6 OTC is equivalent to application of red light over 40 minutes per treatment administration procedure using the Erchonia ZERONA® Z6 OTC with respect to reduction in body circumference attained.

The rationale for evaluating efficacy of the application of violet diodes in this current study is that prior research and preliminary testing has demonstrated that non-inferior (equivalent or superior) results with respect to body circumference reduction can be attained with application of violet light compared with application of red light using the same treatment administration protocol but with lesser treatment administration time per treatment administration – 20 minutes versus 40 minutes, respectively, which is a significant time savings to the patient.

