## STUDY DESIGN

This clinical study is an open-label single-arm non-inferiority design to evaluate the efficacy of the Erchonia Violet ZERONA® Z6 OTC in providing noninvasive body circumference reduction. As such, all enrolled subjects will receive the active study treatment, and therefore, neither randomization to procedure group nor blinding of the subjects nor investigative parties is applicable.

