#### STUDY BLINDING

As all subjects in this study will receive the active procedure administration with the Erchonia Violet ZERONA® Z6 OTC, it is not possible to blind either subjects or investigators (device users).

However, there are two aspects of this study design that assist in supporting elements of blinding:

- (i) The primary efficacy study outcome assessment of body circumference measurements is objective; and
- (ii) As the outcome data from this current study will be comparatively assessed to that of the active treatment group in the predicate device clinical study (the clinical data for the Zerona® Z6 OTC submitted in support of K143007), it is possible to blind the study statistician as to which data set pertains to which study, as the variables for each will be identical. The data from each study will be de-identified and presented to the study statistician simply as 'Group A' and 'Group B' data. The statistician will not be aware of which group A or B contains the current study data and which contains the comparative data. The study statistician will also not be made aware of sample sizes for either analysis group if there is a difference. In this way, study success analysis by the statistician cannot be biased.

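### The comparison with the non-randomised 2014 group takes no account of baseline body size, so a systematic size difference between the studies would be read as a device difference

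*Combined protocol and SAP*

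**What the plan says.** The Study Design section describes an "open-label single-arm non-inferiority design", so every comparison between the violet and red devices is with data from another study.

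Two analyses make that comparison on change in inches:

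- **Primary Efficacy Outcome Evaluation.** The mean change is set against the reference mean, which "was a decrease of 3.72 inches". Success requires the violet result to be "no more than 5% less than the subject group who received treatment with the red diode laser", worked out as -3.53 to -3.91 inches.
- **Supportive Secondary Evaluations (i).** "T-test for independent samples will be performed to compare the mean change in combined circumference measurements across study evaluation", current study against reference group. It is judged on p>0.05 and uses no margin.

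Neither names a covariate, matching or weighting.

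BMI is calculated at qualification, and circumference is measured before the first treatment. Under Study Blinding, de-identified data from both studies go to the statistician as Groups A and B, "as the variables for each will be identical". The Subjects section states that the study population is identical to that of the reference study. The only size criterion is BMI of 30 or less, with no lower limit. Baseline circumference is otherwise used only in a descriptive table by body area. A poolability comparison is planned between the two current sites, but no check of baseline comparability is planned between the two studies.

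**The concern.** Randomisation would make baseline size equal in expectation, but here nothing does. Identical entry criteria define who may enrol; they do not fix the average size of those who do. The current subjects come from these sites' own clients and from people who respond to recruitment materials.

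Taking change from baseline subtracts the starting value, but it does not remove any dependence of the change on that value. If larger people lose more inches from the same treatment, a larger current group would look better than the device deserves. A smaller one could miss -3.53 inches for reasons unrelated to the wavelength. Neither planned analysis can separate the two explanations, although the variable needed to do so is already recorded.

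**Working it through.** **Inputs from the documents.** Reference mean change -3.72 inches; margin 5%; reference responder rate 73% at a 3.0-inch threshold; 22 reference subjects; at least 22 current subjects.

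**Inputs assumed, because the documents do not give them.** Elasticity e (percent change in reduction per 1% of baseline size), 0 to 2. Between-subject coefficient of variation (CV) of baseline circumference, 8% to 10%. Normally distributed change, used to infer an SD.

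**1. Reproduce the plan's range.** 3.72 × 0.95 = 3.534 and 3.72 × 1.05 = 3.906, matching 3.53 and 3.91. The margin is 0.05 × 3.72 = 0.186 inch.

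**2. Shift in mean change from a 5% baseline difference.** Shift = 3.72 × 0.05 × e.

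| e | Shift (inches) | Share of primary margin |
|---|---|---|
| 0 | 0 | 0% |
| 0.25 | 0.047 | 25% |
| 0.5 | 0.093 | 50% |
| 1 (strict proportionality) | 0.186 | 100% |
| 1.5 | 0.279 | 150% |
| 2 | 0.372 | 200% |

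**3. Inferred SD of change.** (3.72 - 3.0) / z(0.73) = 0.72 / 0.613 ≈ 1.175 inches.

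**4. Would the t-test reveal such a shift?** The standard error with 22 per group is 1.175 × √(2/22) = 0.354 inch. The 95% CI half-width on 42 degrees of freedom is 0.715 inch. Power to detect a 0.186-inch difference (two-sided 0.05) is about 8%, so a shift of that size would usually go unnoticed.

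**5. Precision gained by adjustment, under proportionality.** The SD of change explained by baseline is 3.72 × 0.08 = 0.298 to 3.72 × 0.10 = 0.372 inch. The correlation is 0.298/1.175 = 0.253 to 0.372/1.175 = 0.317. The variance reduction is r² = 6% to 10%. The adjusted half-width is 0.715 × √0.936 = 0.69 to 0.715 × √0.900 = 0.68 inch, ignoring the one degree of freedom spent on the covariate.

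**6. Chance imbalance.** The standard error of the relative baseline difference is CV × √(2/22) = 2.4% to 3.0%. At e = 1 this is 3.72 × 0.024 = 0.09 to 3.72 × 0.030 = 0.11 inch. It is one component of the 0.354-inch standard error in step 4, not an addition to it.

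**The case against.** The strongest reply is that the plan asserts an identical population, that nothing in the documents shows the two groups to differ in size, and that adjustment barely helps a comparison this small. It adds that in non-randomised groups a change-score analysis and an ANCOVA can legitimately disagree, that a baseline measured with error leaves residual confounding, and that BMI and circumference overlap as covariates.

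Much of this stands. No imbalance is demonstrated, the precision gain is modest, and possible disagreement between the methods is a good reason to show both results. It is not a reason to leave a recorded baseline variable out of the only comparison between the devices. The asserted identity of populations rests on definitions and cannot guarantee equal body size.

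Four stronger readings are tempting, and the documents do not support them:

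- *A 5% size difference by itself uses up the margin.* That needs strict proportionality, which the documents neither support nor refute.
- *The t-test is biased against its margin.* It has none; the 5% belongs to the primary criterion. Reading non-significance as equivalence is a separate problem that adjustment does not cure.
- *Chance imbalance biases the t-test.* It is already in the standard error. Only a systematic difference between the studies goes unaddressed.
- *Adjustment could cut variance by a quarter.* That needs a correlation of 0.5. Under proportionality with a CV of 8% to 10%, the SD of change would then be 0.298/0.5 = 0.60 to 0.372/0.5 = 0.74 inch, implying about 83% to 89% responders rather than 73%.

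Nor does the plan claim that body size was controlled: its statement that "all other variables of device user, use, and application are held constant" concerns the device and its use, not the subjects.

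**Conclusion.** The point holds as a gap in the analysis, not as a demonstrated bias. Both comparisons with the 2014 group are unadjusted for baseline size, so a systematic size difference would pass into the estimated device difference. For an assumed 5% baseline difference the shift is 0 to 0.37 inch over elasticities of 0 to 2, against a primary margin of 0.186 inch. Where the truth lies in that range cannot be told from the documents.

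The case for adjustment rests on bias. The gain in precision, about 6% to 10% of variance, depends on proportionality, a CV of 8% to 10% and an SD inferred under normality. Feasibility is also inferred: the Study Blinding section speaks of data with identical variables, but does not say in terms that they are individual records or that 2014 baseline BMI is among them.

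**What to change.** 1. In Supportive Secondary Evaluations (i), prespecify an ANCOVA of change in combined circumference on study group and baseline combined circumference, adding baseline BMI if it is in the 2014 data. Report the adjusted between-study difference with its 95% CI as the supportive comparison. The Group A/B masking can stay.
2. Show the unadjusted difference beside it.
3. Add a table comparing baseline combined circumference and BMI (where available) between the two studies.
4. In the Primary Efficacy Outcome Evaluation, show the adjusted estimate next to the primary result as a sensitivity analysis, leaving the success rule as it is.

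The cost is SAP wording and a little more analysis, settled before the two data sets are compared, plus confirmation that individual 2014 records are available.

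The change does not remove unmeasured differences between the studies. Nor does it make 22 per group adequate for the margin: the adjusted half-width stays above 0.6 inch, more than three times 0.186. At an SD of 1.175 inches and one-sided 0.025, 80% power for that margin would need about 627 per group.

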### Sample Size

There will be a minimum of 22 qualified subjects enrolled in and completing this study.

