#### Rationale for Sample Size

Sample size is determined to be identical to the final sample size treated and evaluated in the 2014 Zerona® Z6 OTC comparative study to enable clinically meaningful statistical comparison of outcomes to be performed.

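### The supportive t-test treats p>0.05 as evidence of equivalence, makes no use of the 5% margin, and can report support after the primary criterion has been missed

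*Combined protocol and SAP*

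**What the plan says.** Under Primary Efficacy Outcome Evaluation, "success for the current study will be determined as having been met if the mean change in combined circumference measurements" lies within 5% of the reference mean of -3.72 inches, that is, from -3.53 to -3.91. That rule is applied to the observed mean.

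Supportive Secondary Evaluations then adds two analyses "to provide direct support for the primary efficacy evaluation outcome". For item (i), a "T-test for independent samples will be performed to compare the mean change in combined circumference measurements" between the two studies. Its decision rule is: "A finding of the difference being not statistically significant (p>0.05) will provide statistically significant and clinically meaningful support for the equivalency" of the devices' efficacy. Item (i) has no margin and no confidence interval, and it is not conditional on the primary criterion being met. Item (ii), the responder analysis, does have a 5-point range around the reference rate.

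On size, the Sample Size section states: "There will be a minimum of 22 qualified subjects enrolled in and completing this study". The rationale gives no power calculation: "Sample size is determined to be identical to the final sample size treated and evaluated in the 2014" comparative study, which treated 22 client subjects (Regulatory Background).

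**The concern.** A p-value above 0.05 from a test of no difference means only that the data did not rule out zero. It does not rule out a shortfall larger than the margin. Calling such a result statistically significant support reverses the logic of the test. The rule also rewards imprecision: the noisier the data, the easier it is to satisfy.

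The test cannot inform the primary result in either direction. If the primary criterion is met, p>0.05 is almost guaranteed and adds nothing. If the mean reduction falls short of 3.53 inches, p>0.05 can still occur, and the plan would then report support for equivalency beside a missed primary criterion. The results are meant to support a 510(k) claim of non-inferiority (Indication for Use), so a pre-specified sentence of this kind could carry weight it has not earned.

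**Working it through.** **Inputs.** Reference mean change -3.72 inches and margin 5% (Primary Efficacy Outcome Evaluation). Responder threshold 3.0 inches, with the reference rate given in item (ii): "as the responder rate attained in the reference study was 73" per cent. 22 per group (Sample Size; Regulatory Background).

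**Assumptions.** Equal SDs, normal changes, exactly 22 analysed per group, two-sided 0.05 (the plan does not state sidedness). The SD of change is not given, so a range is shown.

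**The plan's own range.** 3.72 × 0.95 = 3.534 and 3.72 × 1.05 = 3.906, which reproduces -3.53 to -3.91. The margin is 0.05 × 3.72 = 0.186 inch.

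**Central SD.** If 73% of a normal distribution with mean 3.72 lies at or above 3.0, then SD = (3.72 − 3.0)/z(0.73) = 0.72/0.613 = 1.17 inches.

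**Largest observed difference that still gives p>0.05.** t(0.975, 42 df) × SD × √(2/22) = 2.018 × 1.17 × 0.3015 = 0.712 inch, which is 0.712/0.186 = 3.8 margins. The weakest current-study mean that would still count as support is -3.72 + 0.712 = -3.01 inches.

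**Results over a range of SDs.** The third column uses the noncentral t distribution with 42 df and a true difference of 0.372 inch (10% worse, twice the margin). The fourth column is a simulation with the reference mean and SD held at their observed values and a true violet mean of -3.348. It counts trials whose mean falls short of -3.53 and that still give p>0.05.

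| SD (inches) | Weakest mean giving p>0.05 | P(p>0.05), device 10% worse | Primary missed and p>0.05, device 10% worse |
|---|---|---|---|
| 0.5 | -3.42 | 33% | 22% |
| 0.75 | -3.26 | 64% | 57% |
| 1.0 | -3.11 | 77% | 66% |
| 1.17 | -3.01 | 82% | 67% |
| 2.0 | -2.50 | 91% | 64% |
| 3.0 | -1.90 | 93% | 60% |

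**When the conflict disappears.** A mean inside the primary range differs from -3.72 by at most 0.19 inch. That cannot reach p≤0.05 unless SD is below 0.19/(2.018 × 0.3015) = 0.31 inch. Above that SD, meeting the primary criterion guarantees p>0.05, and there is always a band of means that miss it and still give p>0.05. Read one-sided, the threshold SD is about 0.37 inch, and the critical difference at SD 1.17 is 1.682 × 1.17 × 0.3015 = 0.59 inch.

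**Effect of sample size.** With SD 1.17, the reference group fixed at 22 and a device 10% worse, the chance of reported support is 87% with 11 current subjects, 82% with 22 and 78% with 44. Fewer data make the rule easier to satisfy.

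**The case against.** - **It is only secondary.** This stands. Success is decided by the primary rule alone, so the damage is an unsound supporting statement and not a wrong study decision. That limits the severity.
- **The lead-in mentions non-inferiority criteria.** It says the evaluations are judged on significance and/or pre-determined non-inferiority criteria. Only item (ii) is then given such a range, so item (i) still has no margin.
- **A smaller study is not permitted.** Correct: 22 completers is a minimum, and more may be analysed. The sample-size comparison illustrates how the rule behaves; it does not predict this trial. Noisy data remain possible at any size.
- **The central SD is soft.** This also stands. It rests on normality and on a rate from 22 subjects. If 73% is 16/22, its exact 95% interval is about 50% to 89%, which is compatible with SDs from about 0.58 inch upward with no useful upper limit. The probabilities therefore vary widely, and the SD 0.5 row is much milder. The defect lies in the stated rule and does not depend on any one SD.
- **What counts as a miss.** Here it follows Primary Efficacy Outcome Evaluation. The inequality signs under Hypotheses run the other way, which is a separate matter. A mean beyond -3.91 also lies outside the printed range and could give p>0.05.

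**Conclusion.** The concern holds. Item (i) states an invalid inference, and nothing elsewhere in the plan repairs it. Under the assumptions above, with SD about 1.17 inches, a device 10% worse would be reported as supported about 82% of the time (33% to 93% for SD 0.5 to 3.0). In about 67% of trials of such a device the primary criterion would be missed and support still reported (22% to 67% over the same SDs). The SD is inferred and not stated, but the conflict disappears only below about 0.31 inch. This should be corrected before analysis. It does not change how the primary outcome is decided.

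**What to change.** 1. Delete the sentence that reads p>0.05 as support for equivalency.
2. Replace it with: *The between-study difference in mean change in combined circumference (violet minus red; positive means a smaller reduction with violet) will be reported with its two-sided 95% confidence interval and shown against the 0.186-inch margin.*
3. Add: *A non-significant p-value will not be read as evidence of equivalence.*

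Adjustment for baseline combined circumference by ANCOVA is optional and not needed to cure the defect. Study Blinding suggests it is feasible, since both data sets go to the statistician "as the variables for each will be identical". If baseline correlates 0.5 with change (assumed), the half-width would fall only from 0.712 to 0.712 × √0.75 = 0.62 inch.

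**Cost.** SAP wording and one confidence interval; no new data. The sponsor should expect an inconclusive answer. At SD 1.17 the half-width is about 0.71 inch, and the interval would exclude a 0.186-inch shortfall only about 7% of the time even if the devices were truly equal (23% at SD 0.5, 12% at 0.75, 4% at 3.0). More enrolment does not cure this while the reference group stays at 22. Even with unlimited current enrolment the half-width is 1.96 × 1.17/√22 = 0.49 inch, and the chance is Φ(0.186/0.249 − 1.96), about 11%. The sponsor gives up a supporting statement and gains an honest estimate with its uncertainty.
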